2.2.5 Completion

Patient will be considered to have completed the study once the patient completes the 14-day post-discharge interview phone call (+9 days).

2.2.6 Outliers

The data management and statistical analysis teams will identify patients having data values that appear to be potential outliers. These values will be sent to the research coordinators for verification. Clear identification of a value as an outlier will be based on medical judgment as well as on statistical grounds. In the event that outlier values are identified, any analysis using the actual values will be followed by an analysis that reduces the outlier effect.

2.2.7 Missing data

We will continue to collect EHR data (CCHMC Epic and HealthBridge) for the primary outcome for all study participants unless consent is withdrawn. Our approach for handling missing data will be to first assess consent withdrawal rates and evaluate whether or not the rates are very different between the two arms of the trial. If the rates/reasons are similar, we will perform the analysis assuming *Missing Completely at Random (MCAR)*, i.e., the propensity for a data point to be missing is completely random such that there is no relationship between whether a data point is missing and any values in the data

set, missing or observed (missing data are a random subset of the data). If consent withdrawal rates are very different between the two arms of a trial, then our results will be limited by concerns about potential bias. For secondary outcomes of post-discharge coping difficulty and days back to normal subject-reported outcomes collected at the 14-day phone call, missing outcome data could occur for several reasons, such as item nonresponse, lost to follow-up, and data collection errors. Our approach for handling missing secondary outcome data will be to first assess missing patterns/reasons for missing, understand the distribution of missing data, and evaluate any differences between the two trial arms. This will allow us to assess whether an assumption of MCAR (missing data are a random subset of the data) is reasonable or if missingness is conditional on another variable in the dataset, i.e., Missing at Random (MAR). We will use descriptive statistics to compare baseline characteristics of patients with and without missing data. If MAR, we will incorporate variables that are identified to be related to the missingness in the analysis using multiple imputation, as multiple imputation works best when good predictors of outcome are available.

2.2.8 Protocol Violations/Withdrawals

If a study participant is to be excluded/dropped from the study database and/or analysis, the PIs/coordinators will provide to the data management and statistical analysis team the following: 1) the specific reason for dropout (e.g., withdrawal, protocol violation), in as much detail as possible (such as failure to complete the intervention within the time window); 2) who decided that the participant would be excluded; and 3) whether the exclusion involves some or all types of participation.

2.3 Statistical Report Contents

The following section outlines the contents of the final statistical analysis. For all analyses, baseline is defined as the measurement prior and closest to the date of discharge from the index hospitalization event. Patients who are randomized will be analyzed in the groups to which they were allocated regardless of actual intervention received.

2.3.1 Description of study population

Sample size:

The total number of patients who are screened, consented, randomized, and withdrawn will be given. A summary of patients with protocol violations, such as failed nurse phone call, or who were withdrawn will be provided.

Demographics and Clinical Characteristics, Patient and Parent:

Demographic and clinical characteristics as measured at baseline will be summarized by trial arm. Variables to be summarized are: child age, only child indicator, first hospitalization indicator, parent or caregiver age, race/ethnicity, education, marital status, household income, employment status, primary payor, financial strain, access to primary care, census track poverty (high vs. low percentage below poverty), state of residence (Ohio vs. Kentucky). Primary discharge diagnosis ICD9 or ICD10 codes will be categorized using the AHRQ CCS algorithm. Variables will be summarized using descriptive statistics appropriate for each type of data item.

Baseline characteristics with large differences between groups will be included in analyses evaluating the effectiveness of the intervention.

2.3.2 Primary outcome analysis

Primary outcome: unplanned re-hospitalization and/or any emergency/urgent care visits within 30 days of hospital discharge

For the primary outcome, the dependent variable will be a dichotomized indicator of any occurrence of unplanned re-hospitalization and/or any emergency/urgent care visits within 30 days of hospital discharge recorded in CCHMC Epic or Healthbridge for non-CCHMC events. Differences between intervention and control groups on this outcome will be evaluated using logistic regression with the stratification variables (census tract poverty and state of residence). Other potential covariates (e.g. baseline characteristics of age, first hospitalization, only child, caregiver education, with large differences between groups) will be included in a secondary analysis model evaluating the effectiveness of the intervention.

2.3.3 Secondary outcome analyses

Post-Discharge Coping Difficulty Scale (PDCDS)

Post-Discharge Coping Difficulty Scale (PDCDS) will be measured during the 14-day post-discharge phone call. The PDCDS uses an 11 point scaling format (0-10). Higher scores represent greater coping difficulty. A total score will be computed as describe here:

Items 8, 9, 10 a and 10 b will be reverse scored

Total scale score = mean of 1+2+3+4+5+6a+7+8+9+10a+10b (missing items ignored) multiplied by 10 to give a score range of 0 to 110.

Item 6b is included for comparison with 6a and will not be included in the total score. The distribution of this outcome will be assessed for normality; if appropriate, we may apply a transformation or utilize a suitable link function. Differences between intervention and control groups on this outcome at 14-day post-discharge will be evaluated using a generalized linear model with the stratification variables (census tract poverty and state of residence) and other potential covariates included in the model.

Back to normal routine perceived by caregiver - number of days 0 to >=14

The distribution of this outcome will be assessed for normality; if appropriate, we may apply a transformation or utilize a suitable link function. Differences between intervention and control groups on this outcome at 14-day post-discharge will be evaluated using a generalized linear model with the stratification variables (census tract poverty and state of residence) and other potential covariates included in the model.

- Secondary healthcare re-utilization measures:
 - Type specific, hospital and ED admissions only, within 30 days of hospital discharge.
 (dichotomized as any hospital/ED reported event through the HIE or CCHMC EPIC)
 - Early re-utilization within 14-day post-discharge (HIE data or CCHMC Epic or parent report)

These secondary healthcare re-utilization measures will be analyzed following the same approach described for the primary outcome.

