Initial Questionnaire: Face-to-face interviews will be conducted in the hospital with the parent or caregiver at the time of enrollment. We will assess demographic characteristics, such as race, ethnicity, and age for both the parent/caregiver and patient. We will assess parent or caregiver marital status, education, household income, employment status, resilience, and parental activation. In addition, we will assess the ACE (adverse childhood experience) score of parents ages 18 years or older. The ACE score is a measure of childhood trauma that has occurred in the past. It does not indicate current exposure. Higher scores (ACE score greater than or equal to 4) have been associated with poorer adult health outcomes. Parental ACE scores have demonstrated an association with risk for childhood adversity in an outpatient setting. The questions encompass all forms of childhood trauma, including whether the participant was exposed to a household member that was depressed or suicidal or if the participant had been abused as a child. The ACE questionnaire will be provided as a handout for the study participant to fill out. It will be supplemented with a handout with the contact information of an inpatient social worker. It will be returned by the study participant in a sealed envelope to the research coordinator. It may be left blank by the study participant if they choose not to answer the questions. We will also assess the patient's medical history and their access to primary care, as well as other variables that arise from Aims 1 and 2. Survey data will be entered into a password protected electronic database.

Aim 3 Nurse Home Visit Intervention: The intervention for Aim 3 is a revised nurse home visit. This intervention will build upon the baseline nurse home visit program by incorporating approaches to effectively address barriers to transition as determined in Aims 1 and 2. The current program involves a *single* nurse home visit within 96 hours after discharge and includes

physical and self-management assessment with the goal of ensuring patient stability and caregiver confidence. While we expect that many elements and processes of the current nurse home visit will remain intact, in Aim 1 we will be assessing current users' perceptions of the services as well as better defining the patient- and family- desired outcomes. In Aim 2, we will test small changes to the home visit elements and processes as informed by Aim 1 results.

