Aim 4 Nurse Phone Call Intervention: The intervention for Aim 4 is a revised nurse phone call. This intervention will closely resemble the existing nurse home visit intervention currently being studied. The current program involves a *single* nurse home call within 96 hours after discharge and includes physical and self-management assessment with the goal of ensuring patient stability and caregiver confidence. While we expect that many elements and processes of the current nurse home visit will remain intact, in the optimization phase we will be assessing early users' perceptions of the and we will test small changes to the phone call elements and processes as informed by early testing.

Follow-up Questionnaire: A follow-up questionnaire to assess 14-day post-discharge outcomes will be conducted in both the control and intervention groups 14-30 days post-discharge. All efforts will be made for the follow-up questionnaire to be completed with the same parent or caregiver who completed the initial questionnaire. If this is not possible we will re-collect demographic information for the secondary parent or caregiver completing the follow-up questionnaire. We will collect the primary outcome measures of unplanned post-discharge utilization, as well as the secondary outcomes defined during the focus groups in Aim 1, and will re-measure the parental activation. Survey data will be entered into a password protected electronic database.

For approximately 40 of our patients, the research coordinator asked the parent's race as opposed to the patient's race for Aim 3 only. We are requesting permission to contact these participants via text message and phone call to ask the patient's race. We will also be asking the patients some questions regarding their experience with the intervention (nurse home visit) in Aim 3. We are asking these additional questions in order to use this feedback for future research studies as well as to help the flow of the call.

Medical Record Review: We will receive all enrolled patients 30-day reutilization (readmission and ED revisit) data from HealthBridge. HealthBridge is an organization that receives admission and emergency room data from hospitals throughout the Greater Cincinnati area. This will allow us to track reutilization outcomes at 30-days, while completing the call with families at 14-days. This will ensure that we have similar data for our primary outcomes from all patients.

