For our secondary outcomes, allowing for 11% noncompliance and 5% attrition, the sample size will achieve 80% power to detect a mean difference of 3.1 points on the PDCS between control and phone intervention groups assuming a standard deviation of 16 points for both groups. The sample size will achieve 80% power to detect a mean difference of 0.98 days for return to normal routine assuming a standard deviation of 5 days for both groups. Both estimates assume alpha 0.05 and a 2-sided test.

Post-Hoc Analysis

Qualitative Analysis:

The team will meet to discuss the interviews and identify ideas, concepts, and themes of the interviews. Weekly meetings will be held until the completion of the interviews allowing for ongoing scrutiny and feedback about the interpretation of the data. Interview and focus group transcripts will be de-identified and reviewed by investigators and lead CRC trained in qualitative data analysis. The investigators and lead CRC will meet on a regular basis to discuss the transcripts, and will define and organize themes in an iterative fashion. The results of these interviews and focus groups will provide a deeper understanding of our results.

Readmission Analysis:

We will compare the percentage of readmissions designated as potentially preventable in those patients randomized to the intervention in Aim 3 compared to the percentage of readmissions designates as potentially preventable in those patients randomized to the control group in Aim 3

FACILITIES AND PERFORMANCE SITES

All research activity will occur within the CCHMC Burnet Campus and Liberty Campus inpatient wards. Other CCHMC sites such as College Hill Campus will not be included.

POTENTIAL BENEFITS

The potential benefits of the proposed research are to improve the nurse home visit and phone call program and inpatient to outpatient transitions experiences for families, nurses, and PCPs. Subjects receiving home visits or phone calls could potentially benefit directly from this intervention. Additionally, information obtained from the research findings may benefit other families in the future. The risk of loss of confidentiality is reasonable in relation to the anticipated benefits to the subjects, especially with the appropriate precautions noted.

POTENTIAL RISKS, DISCOMFORTS, INCONVENIENCES AND PRECAUTIONS

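### The SAP does not prespecify baseline caregiver resilience and parental activation as covariates for coping difficulty, and its only stated covariate rule is chance imbalance rather than prognostic value

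*SAP*

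**What the plan says.** The enrolment questionnaire shared by Aims 3 and 4 (Protocol, Study Procedures, Initial Questionnaire) states: "We will assess parent or caregiver marital status, education, household income, employment status, resilience, and parental activation". The interview takes place in hospital, and the protocol's Aim 4 design section randomises after discharge, so both scales are pre-randomisation measures. The follow-up questionnaire "will re-measure the parental activation".

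PDCDS is collected only at the 14-day call (SAP 2.3.3). Its model is a "generalized linear model with the stratification variables (census tract poverty and state of residence) and other potential covariates included in the model". The further covariates are not listed there. Two other places bear on them:

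- SAP 2.3.1: "Baseline characteristics with large differences between groups will be included in analyses evaluating the effectiveness of the intervention".
- SAP 2.3.2, for the secondary model of the primary outcome, gives as examples "baseline characteristics of age, first hospitalization, only child, caregiver education, with large differences between groups".

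The variables that 2.3.1 will summarise by arm include "employment status, primary payor, financial strain, access to primary care, census track poverty", but neither resilience nor activation. SAP 2.2.7 says that, if data are judged missing at random, "we will incorporate variables that are identified to be related to the missingness in the analysis using multiple imputation"; it names no variables. The protocol's own Aim 4 analysis text names neither scale. Its sample-size text claims "80% power to detect a mean difference of 3.1 points on the PDCS".

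**The concern.** In a randomised trial a baseline covariate improves precision when it predicts the outcome, whether or not the arms happen to differ on it. A rule based on observed imbalance therefore selects on the wrong property. It also leaves the model to be settled after the arms have been compared.

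The point matters most for PDCDS because there is no earlier value on the same scale to adjust for. Resilience and activation are, on their face, the collected caregiver measures closest to coping, although the documents offer no evidence on how well they predict it. They are missing from the 2.3.1 list, so the plan does not call for the arm comparison that would trigger its own imbalance rule for them.

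PDCDS is one of the two outcomes in working hypothesis 2 and has its own power statement. What is at stake is the width of its confidence interval, and a model that is not fully fixed in advance. Bias is not at issue.

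**Working it through.** **Inputs.** From Protocol, Data Analysis/Methods, Aim 4: SD 16, difference 3.1, two-sided alpha 0.05, 750 control and 450 phone, 11% noncompliance, 5% attrition. Not in the documents: how much PDCDS variance the two scales explain. Below, R² is an assumption. It means the share of the variance left after the covariates already planned, with 16 taken as the SD at that point.

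**Step 1: reproduce the stated figure with no covariates.**

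- After attrition: 750 × 0.95 = 712.5 and 450 × 0.95 = 427.5.
- Difference diluted by noncompliance: 3.1 × 0.89 = 2.759.
- SE = 16 × √(1/712.5 + 1/427.5) = 0.979.
- Power = Φ(2.759/0.979 − 1.960) = Φ(0.859) = 80.5%.
- Detectable difference at 80% power = (1.960 + 0.842) × 0.979/0.89 = 3.08.

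Both agree with the protocol's 80% and 3.1 points, so the stated power rests on no adjustment.

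**Step 2: add the two scales.** SE becomes 0.979 × √(1 − R²), in the same formulas. The equivalent gain in sample size is 1/(1 − R²).

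| Assumed R² | SE relative to step 1 | Detectable difference | Power at 3.1 | Equivalent sample |
|---|---|---|---|---|
| 0 | 1.000 | 3.08 | 80.5% | × 1.00 |
| 0.02 | 0.990 | 3.05 | about 81% | × 1.02 |
| 0.05 | 0.975 | 3.00 | 82.4% | × 1.05 |
| 0.10 | 0.949 | 2.92 | 84.4% | × 1.11 |
| 0.20 | 0.894 | 2.76 | 88.3% | × 1.25 |

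**Step 3: keep a separate issue separate.** SAP section 1 plans 900 patients at 1:1. At 450 per arm, SE = 16 × √(2/427.5) = 1.094 and power with no covariates is Φ(2.759/1.094 − 1.960) = 71.3%. For R² of 0.05, 0.10 and 0.20 it becomes 73.5%, 75.7% and 80.5%. The fall from 80.5% to 71.3% comes wholly from the conflict between 1,200 patients in the protocol and 900 in the SAP.

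These figures assume a linear model on the original scale, whereas SAP 2.3.3 also allows a transformation or another link. No calculation was made for days back to normal routine.

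**The case against.** A reader might infer that the SAP excludes the two scales from every model. The documents do not support that. The wording in 2.3.3 is open and carries no imbalance condition of its own, the list in 2.3.2 is given as examples for a different outcome, and the imputation text in 2.2.7 would admit any variable related to missingness. What can be said is that the scales are not prespecified, the covariate set is undefined, and no stated rule would choose them for prognostic value.

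A reader might also infer that the trial certainly loses precision. That is not shown either: no correlation with PDCDS is given, and the gain could be close to zero. The proper comparator is the planned model, which already contains poverty and state and may contain more. This is why R² above is incremental, and a scale's total R² could overstate the gain.

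The questionnaire text is shared with Aim 3, where activation is a secondary outcome, and no instrument or scoring rule appears for either scale. The sponsor should confirm that the Aim 4 analysis dataset carries both scores. The text does, however, stand under a heading that covers both aims.

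Finally, the planned comparison is valid as it stands. That is right, and it limits the point to efficiency and to fixing the model in advance.

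**Conclusion.** The point holds as a minor improvement to one secondary analysis. Two pre-randomisation caregiver scales that plausibly relate to coping are collected but not prespecified in any SAP model, and the only stated selection rule is chance imbalance. At 750/450, an incremental R² between 0.05 and 0.20 would add about 2 to 8 percentage points of power; near zero it would add essentially nothing. The range is assumed. The 71.3% at 450 per arm should not be read as the cost of leaving the scales out, since it follows from the sample-size conflict.

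**What to change.** Before outcome data by arm are seen, write the PDCDS model in SAP 2.3.3 as treatment, census tract poverty, state, continuous baseline resilience and continuous baseline parental activation, plus any other named covariates chosen for prognostic value. Child age, first hospitalization, only child and caregiver education are candidates and should not be dropped without evidence. Include all of them whether or not the arms differ. Use only the enrolment activation score as a covariate, because the follow-up score is measured after randomisation. State the instrument and scoring of each scale.

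Add both scales to the 2.3.1 baseline list and to the 2.2.7 imputation model, and impute missing baseline scores so that no family is dropped. The same covariates may be used for days back to normal routine, with no gain claimed. If the analysis has already been done, report the adjusted model as a justified deviation under 2.1.1.

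The cost is SAP wording, two degrees of freedom among roughly 855 (900 × 0.95) to 1,140 (1,200 × 0.95) analysed families, and the handling of occasional missing baseline scores. No new data and no extra patients are needed, provided that both scores were collected as the protocol states.

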2.3.4 Subgroup analyses

Exploratory prespecified subgroup analyses will be conducted by classification of subjects based on financial strain (high strain vs. low/moderate strain), access to primary care (high vs. moderate vs. low access), caregiver education (high school graduate vs. no high school degree), and publically insured, then evaluate the effectiveness of the nurse phone call within each subgroup using the approach described above for each outcome measure. Heterogeneity of treatment effects will be based on tests for interaction between subgroup level and treatment group and will be presented with effect estimates (including confidence intervals) within each level of the subgroup measure. The following outcomes will be evaluated: primary unplanned 30-day re-utilization and secondary outcome of days back to normal.

Financial/social strain- 10 categorical questions measured at baseline. A total financial strain score will be computed by summing the items with the top-box score for Likert items and yes for yes/no items. The distribution of the total scores will be obtained and dichotomized based on the top tertile.

- O At the end of the month, do you generally end up with...? (Likert 1-3, 3 as top-box)
- O During the past 12 months was there a time when you wanted to find work but were not able to?
- During the past 12 months, was there a time when your household did not pay the full amount of rent or mortgage?
- O During the past 12 months, has your household not paid the full amount of any of the utility bills for electricity, heating or water?
- o If you or your household had a problem with which you needed help (for example, child care, sickness or moving), how much help would you expect to get from family or friends living nearby? (in the same general region/city?) (Likert 1-5, 4 or 5 as top-box)
- O Do you or your spouse/partner own your home? (reverse score no)
- O Do you or your spouse/partner own a car, truck or van? (reverse score no)
- o If you needed financial help during the next year, do you think you could count on people (family, friends, a bank or any source) to loan you \$1000? (reverse score no)
- During the past 12 months, have you borrowed money from friends or relatives because of financial circumstances or difficulties?
- During the past 12 months, have you or moved in with other people because of financial circumstances or difficulties?

Access to a primary care – measured at baseline using the Access subscale of the Parent's Perceptions of Primary Care (P3C) Scale. Responses are scored on a 5-point Likert-type scale (0=never to 4=always), with higher scores indicative of better primary care access for both routine and sick care. Items will be transformed to a 0 to 100 scale, with 100 being best, as follows: 0 = 0, 1 = 25, 2 = 50, 3 = 75, and 4 = 100. A total scale score will be computed as the mean of the nonmissing items. The total score will be categorized as always (100), almost always (75-99), and sometimes/often/never adequate (<75).

- o Is it easy for you to travel to the doctor?
- Can you see the doctor as soon as you want for routine care (check ups, physicals) for the patient?
- o If the patient is sick, can you see the doctor within one day?
- Can you get help or advice on evenings or weekends?

Caregiver education – measured at screening. Caregiver education will be dichotomized as high school graduate vs. no high school degree.

Publically insured – measured at screening. Caregiver reported primary insurance will be dichotomized as public vs. all others.

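### Effect modification by financial strain and primary-care access is tested only through groups; testing the continuous scores would keep information that the cuts discard

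*SAP*

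**What the plan says.** SAP 2.3.4 introduces the analyses with "Exploratory prespecified subgroup analyses will be conducted by classification of subjects". The test is specified as: "Heterogeneity of treatment effects will be based on tests for interaction between subgroup level and treatment group". Effects with confidence intervals are also to be shown within each level. Two outcomes are covered: "The following outcomes will be evaluated: primary unplanned 30-day re-utilization and secondary outcome of days back to normal".

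Two of the four modifiers are scores.

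- **Financial strain** rests on "10 categorical questions measured at baseline". The scoring rule is "A total financial strain score will be computed by summing the items with the top-box score for Likert items and yes for yes/no items", which makes the total an integer from 0 to 10. Then: "The distribution of the total scores will be obtained and dichotomized based on the top tertile".
- **Access to primary care** is the mean of four items, each rescaled to 0-100. Then: "The total score will be categorized as always (100), almost always (75-99), and sometimes/often/never adequate (<75").

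Neither the SAP nor the protocol plans an interaction with either score left continuous. Neither gives a distribution for the scores or a power figure for any interaction test. For strain, the SAP does not say how ties at the tertile are assigned or how an unanswered item is scored. For the coping scale (SAP 2.3.3) and the access scale (SAP 2.3.4) it does say that missing items are left out of the mean.

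**The concern.** An interaction test in a trial sized for main effects starts with little power. Replacing an ordered score by a few groups treats everyone within a group as alike, so any change in effect within the group is lost to the test. If benefit rises or falls steadily with strain or access, the planned test is more likely to miss it than a test on the same data with the score left whole. A null result would then say less about heterogeneity than it could.

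The strain grouping is also not fully defined. An 11-value score need not have a cut that isolates one third of families, so two analysts could form different high-strain groups from the same data.

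**Working it through.** **The plan's own figures first.** No interaction power is stated, so the nearest check is the protocol's Aim 4 sample size (Data Analysis/Methods). I treat the 11% noncompliance as dilution of the effect, at two-sided alpha 0.05.

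- Reutilization, 750 control and 450 phone: diluted rate 0.20 − 0.89 × 0.071 = 0.137 against 0.20; power 80.4%. The stated 80% reproduces.
- Days to normal, SD 5, 5% attrition: difference 0.89 × 0.98 = 0.872; SE = 5 × √(1/712.5 + 1/427.5) = 0.306; power = Φ(0.872/0.306 − 1.960) = 81%. This reproduces too.

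**Information kept by a cut.** For a linear modifier, the information kept is R = between-group variance of the score ÷ its total variance. R does not depend on the sample size.

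- *Normal score, top third against the rest.* The cut is at c = 0.431 and φ(c) = 0.3636. R = φ(c)² / (1/3 × 2/3) = 0.1322/0.2222 = 0.595, a loss of 40.5%.
- *Integer 0-10 score.* I assumed beta-binomial scores with mean 1 to 5 and inter-item correlation 0 to 0.4 (48 scenarios), each cut nearest the top third. Example with mean 2 and correlation 0.2: variance 10 × 0.2 × 0.8 × (1 + 9 × 0.2) = 4.48. A cut at 3 or more puts 32.7% in the high group, with group means 4.57 and 0.75. R = 0.327 × 0.673 × 3.82² / 4.48 = about 0.715.
- Over the grid, R runs from 0.535 to 0.780: a loss of 22% to 47%, median 31%. The loss is a third or more in 29% of scenarios.

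**Power after the split.** A continuous-score test with 80% power has expected z = 1.960 + 0.842 = 2.802. After the split, power = Φ(2.802√R − 1.960).

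| Score | R | Power |
|---|---|---|
| Continuous | 1 | 80% |
| Count, best case | 0.780 | Φ(0.514) = just under 70% |
| Count, median | 0.69 | Φ(0.367) = 64% |
| Normal | 0.595 | Φ(0.201) = 58% |
| Count, worst case | 0.535 | Φ(0.089) = 54% |

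For the normal score, recovering the loss would need 1/0.595 = 1.68 times as many patients. Simulation (900 patients at 1:1 as in SAP section 1, 3,000 runs) agrees: 79% falls to 57% for a normal score, 80% to 66% for a count with mean 3, and 79% to 64% for a count with mean 2 (both with correlation 0.2).

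**Access score.** Four items scored 0-4 give a 0-16 total, cut by the SAP's bands at 16, 12-15 and 11 or less. For assumed means of 10 to 15 and correlations of 0.1 to 0.4, R is 0.608 to 0.855, a loss of about 15% to 39%. The grouped test has 2 df (critical value 5.991). The noncentrality 7.849 that gives 80% on 1 df becomes 7.849 × R, so power is about 48% to 64%. Part of this is the extra degree of freedom: even at R = 1, the 2-df test has about 71%.

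**Absolute scale, days to normal.** With 427 per arm (450 less 5%) and SD 5, the SE of the arm difference in slope per SD of strain is 5 × √(2/427) = 0.342 days. Power of 80% on the continuous score therefore needs 2.802 × 0.342 = 0.96 days per SD. At half that gradient, power is Φ(1.401 − 1.960) = 29% continuous, against 18% to 24% after the split over the grid. At a quarter of it, both tails together give 11% against about 8% to 10%.

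**Ties.** For a Poisson count with mean 1.5, the two cuts nearest a third label 44% or 19% as high strain. At means 1, 2 and 3 the nearest cut gives 26%, 32% and 35%. In the beta-binomial grid the high group is 22% to 46%.

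**The case against.** The strongest case against acting is that these analyses are labelled exploratory, already have a formal interaction test with intervals by level, and decide nothing primary or secondary. The access bands are fixed in advance and carry meaningful labels. The 80% starting point is also generous: it needs the effect to shift by 0.96 days per SD of strain, nearly the whole 0.98-day design effect. For smaller gradients, heterogeneity will usually be missed by either method. All of that stands. It limits the weight of the point but does not make the grouped test the better one.

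Some stronger readings are tempting, and the documents do not support them.

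- *At least a third of the strain information is lost.* No document gives the score's distribution. The 40% figure needs a near-normal score, and most of the count scenarios lose less than a third.
- *A skipped strain item is counted as no strain.* The SAP is silent. The total could equally be set to missing. The items come from an in-person baseline interview, so heavy nonresponse cannot be presumed.
- *The sample-based cut biases the test.* It uses baseline scores only, not outcomes, so it does not.
- *High-strain groups will be far from a third.* The 44% or 19% case is one assumed mean; at others the nearest cut comes close to a third.

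**Conclusion.** The point holds as a modest, inexpensive improvement. SAP 2.3.4 tests effect modification by strain and access only through groups. For a roughly linear modifier, that costs roughly a quarter to just under a half of the strain score's information, and power falls from 80% to between about 54% and just under 70%. For access, 80% falls to about 48-64%.

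These sizes rest on assumed score distributions and on linearity. If the true modification were a step at the chosen cut, the strain split would lose nothing. Absolute power was worked out only for days back to normal, and it is low under either method when the gradient is modest. The missing tie and item-nonresponse rules are gaps in detail, not demonstrated errors.

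**What to change.** In SAP 2.3.4, make arm × continuous strain score and arm × continuous access score (1 df each) the heterogeneity tests for the two stated outcomes. Add a quadratic or spline term for each as a linearity check. Keep the stated groups to display effects with confidence intervals.

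As a side clarification, state how ties at the strain tertile are assigned and how unanswered strain items are scored, for example by prorating over the answered items, in line with the access scale. The documents supply no value for a fixed strain cut-point, so none is proposed.

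The cost is a change of wording, with no new data. The downside is small: the 1-df test assumes a roughly linear gradient, and the check on that assumption will itself have limited power. If the analyses have already been run, the continuous tests can be added and reported as a deviation under SAP 2.1.1.
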